12.3 Phone and Other Media Follow-up

General procedures: At Study Visit 1, subjects and study staff will define optimal times and phone numbers for the protocol-specified phone contacts to encourage compliance with study procedures.

During the follow-up visits, the subject will receive:

- Reminder of appropriate study drug dose for the stage of the protocol.
- Reminder to maintain study dosing diary and discussion regarding dosing compliance
- Encouragement of activity within the limits of their HF symptoms
- Confirm plans for future study visits
- Confirm need to bring study drug and dosing diary to future study visits.

13 OUTCOME DETERMINATIONS

13.1 Primary Endpoint

The proportional change from baseline in the AUC for NT-proBNP levels measured at 2, 4, 8, 12 and 24 weeks.

13.2 Secondary Endpoints

1. Days alive and out of hospital at 6 months, not listed for transplant (status 1A, 1B or 1-4) or undergoing transplant, implanted with an LVAD, maintained or started on continuous inotropic therapy for ≥ 7 days, or has had two hospital admissions for HF (other than the index admission*). If a patient meets the pre-specified secondary endpoint of 2 hospital admissions for heart failure (other than the index admission), the patient can remain on study drug or be started on open label sacubitril/valsartan, at the treating physician's discretion, while remaining in the trial.

*The days alive and out of hospital will end on the day of the second readmission.

2. Tolerability measured as:
 - a) Number of subjects achieving a target dose of 25%, 50% or 100% of valsartan or LCZ696
 - b) Number of subjects developing hypotension (SBP ≤ 85 mmHg) with symptoms
 - c) Number of subjects developing worsening renal function (eGFR < 20 ml/min/1.73 m²)
 - d) Number of subjects developing moderate (≥ 5.5 mmol/L) or severe (≥ 6 mmol/L) hyperkalemia

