## 10.2 – Secondary Endpoint #2

Endpoint Description: Tolerability measured as number of subjects achieving a target dose of 25%, 50% or 100% of valsartan or LCZ696, using the pre-COVID-19 population.

Response Variable Definition: Due to limited documentation concerning reasons for dose reduction, four versions of this endpoint will be calculated:

- 1) maximum study drug dose started (including 0),
- 2) dose patient took for the most number of days (including 0),
- 3) last dose patient was taking (including 0), and
- 4) last dose patient was taking (excluding 0).

There are 4 ordered values possible based upon the coding of the responses. Each response will be coded to represent 0% of target (no drug), 25% of target (50 mg LCZ696/40 mg Valsartan), 50% of target (100 mg LCZ696/80 mg Valsartan) or 100% of target (200 mg LCZ696/160 mg Valsartan). The number of evaluable days will be based on time from randomization to earliest date of Week 24, Death, Consent Withdrawal, or Last Contact.

Additional Covariates in Addition to Randomized Treatment: atrial fibrillation status at time of randomization

Handling of Dropouts and Missing Data: No adjustment will be made for missing data.

Sensitivity Analysis: Re-calculate the endpoint analysis using the original ITT population.

Statistical Tests: An ordinal logistic regression model (PROC LOGISTIC in SAS) will be used to estimate and statistically compare whether there is differential study drug dose achievement between the treatments.

Interpretation of Treatment Comparison: More patients achieving/tolerating higher doses indicates better tolerance of LCZ696 versus Valsartan.

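### SAP 10.2 has no rule for the permitted switch to open-label sacubitril/valsartan, so two of its four dose-tolerability versions would score a switch as 0% of target and read it as poor tolerance

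*Protocol*

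**What the plan says.** Protocol 13.2, under the first secondary endpoint, allows a change of treatment after two HF admissions other than the index one: "the patient can remain on study drug or be started on open label sacubitril/valsartan". The choice is the treating physician's, and the patient remains in the trial.

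SAP 10.2 defines dose achievement as a tolerability endpoint in four versions, because reasons for dose reduction were poorly documented:

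1. the highest study-drug dose started;
2. the dose taken on the most days;
3. the last dose, counting zero;
4. the last dose, leaving out zero.

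On coding it says "Each response will be coded to represent 0% of target (no drug"), followed by 25%, 50% and 100% of target. On the window it says "The number of evaluable days will be based on time from randomization to earliest date of Week 24, Death, Consent Withdrawal, or Last Contact". On reading the result it says "More patients achieving/tolerating higher doses indicates better tolerance of LCZ696 versus Valsartan". It makes no adjustment for missing data and does not mention open-label sacubitril/valsartan.

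**The concern.** The switch is opened by an efficacy event, a second HF admission, and not by failure to tolerate the dose. SAP 10.2 nevertheless keeps counting study-drug dose up to Week 24 for a switcher. Once blinded drug has been replaced, that dose is naturally recorded as zero. The patient may be taking the test drug at full dose and still fall in the no-drug category, which the SAP reads as poor tolerance.

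Death is handled differently. It ends the window, so a patient who dies on blinded drug keeps the last dose taken. For SAP Secondary Endpoint #1, the second HF admission has its own explicit rule.

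What is at stake is the meaning of the tolerability comparison. If one arm has more second HF admissions and hence more switches, versions 2 and 3 turn part of an efficacy difference into an apparent tolerability difference.

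**Working it through.** **Is a switcher's study-drug dose zero?** Protocol 13.2 presents study drug and open-label drug as alternatives. Protocol 10.10 bars ARBs other than blinded study drug, so open-label product is not study drug. SAP 10.2 version 1 names study drug explicitly. Zero after a switch is therefore the natural reading, although the SAP does not state it.

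**Each version applied to a patient who stops blinded drug on day T, switches and does not restart.** Week 24 is day 168.

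- Version 1, "maximum study drug dose started (including 0"): a later switch cannot lower a maximum. Not affected.
- Version 2, "dose patient took for the most number of days (including 0"): zero wins when days off exceed days on any one dose.
  - One dose throughout: 168 − T > T, so T < 84.
  - Titrated at weeks 2 and 4, with the top dose from day 28: 168 − T > T − 28, so 2T < 196 and T < 98.
  - Affected only for switches before about day 84 to 98.
- Version 3, "last dose patient was taking (including 0"): scored 0%.
- Version 4, "last dose patient was taking (excluding 0"): not scored 0%.

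**Size.** The documents give no figure for dose achievement, second HF admissions or switches, so there is no planning figure to reproduce. The nearest is in Protocol 16.2: death or first HF re-admission in 40% on valsartan, against 25% or 30% on LCZ696. That is a different and commoner event.

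Inputs to the illustration:

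- 335 patients in the pre-COVID-19 population (SAP 3), split 168 vs 167 on the assumption that 1:1 held.
- Two-sided 0.05 (SAP 4).
- Identical true tolerance in both arms (assumed): 0/25/50/100% of target in 15/25/25/35% of patients.
- A fraction s of each arm is moved to 0% by switching (assumed), so P(0%) = 0.15 + 0.85s.
- A tie-corrected rank test stands in for the ordinal logistic model, without the atrial fibrillation covariate; 60,000 simulated trials per row.

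| Scored 0% through switching, LCZ696 vs valsartan | P(0%), LCZ696 vs valsartan | Chance of falsely favouring LCZ696 |
|---|---|---|
| none | 15.0% vs 15.0% | about 2.5% |
| 2% vs 4% | 16.7% vs 18.4% | about 4.6% |
| 4% vs 8% | 18.4% vs 21.8% | about 8% |
| 6% vs 12% | 20.1% vs 25.2% | about 13% |

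Equal rates (2% vs 2%, 6% vs 6%) left the figure at about 2.5%. With a base of 10/30/25/35% the three unequal rows gave about 4.9%, 8% to 9%, and 14%.

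A separate run on that second base fitted the proportional-odds model to the expected proportions and simulated 3,000 trials. For version 3, switch rates of 5% vs 5% gave an odds ratio of 1.00, 2% vs 5% gave 1.09, and 3% vs 8% gave 1.16. Two-sided rejection was 4.6%, 6.9% and 11.6%. With zeros excluded, as in version 4, rejection stayed at about 5% in the same scenarios.

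The simulated rates apply in full to version 3. In version 2 only early switches count, so the effect there is smaller for the same total switch rate.

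**The case against.** The strongest reply is that the SAP already covers this. It runs the last dose with and without zeros precisely because reasons for stopping are unclear, so comparing versions 3 and 4 shows whether zeros drive a difference. Version 1 is closest to the endpoint's own wording and is untouched. Version 3 can be defended as an all-cause measure, in line with the intention-to-treat statement in Protocol 16.1. Protocol 12.2 also asks for an attempt to restart study drug after any stop, so a zero need not be final.

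Much of this stands, and it limits the point to two versions. It does not remove the point. Version 4 leaves out every zero, including true intolerance stops, and version 1 ignores every later reduction. No version separates a switch for worsening HF from a stop for intolerance. An all-cause reading of version 3 would be reasonable, but the SAP interprets the result as tolerance.

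A reader might infer more than the documents support:

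- That the SAP states a switch is scored 0%. It does not; this is inferred from the window and the coding. If open-label tablets were counted instead, a valsartan-arm patient could be credited with target dose for taking the test drug, so a rule is needed either way.
- That the same happens at LVAD implantation or transplant. Neither document says study drug stops then.
- That the endpoint as a whole is biased towards LCZ696. That would need all four versions to be affected and switching to be commoner on valsartan. Two are not affected, and no switch rates are given.

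**Conclusion.** The point holds as a gap in SAP 10.2. The protocol permits a switch for which the SAP has no coding rule, and following the stated window leads version 3, and version 2 for early switches, to record it as 0% of target and read it as poor tolerance.

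The effect depends on switch rates differing between arms. With equal rates there is none. If valsartan patients switch twice as often, at the assumed 2% vs 4% to 6% vs 12%, the chance of a false finding in favour of LCZ696 rises from 2.5% to about 5% to 13% in the affected versions. More switching on LCZ696 would bias the other way. These figures rest on assumed dose distributions, assumed switch rates, and switchers not restarting blinded drug.

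This is a secondary tolerability endpoint and the primary analysis is not touched. The change is still worth making, because the misreading is systematic and cheap to prevent.

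**What to change.** In SAP 10.2, add the start of open-label sacubitril/valsartan to the dates that end the evaluable dosing period. Score the blinded dose in effect immediately before the switch, and keep 0% where blinded drug had already been stopped for another reason. Without that last condition, a patient who stopped for hypotension weeks before switching would regain a non-zero score. Report the number of switchers by arm beside the four versions.

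The cost is one or two sentences in the SAP and one extra date in the derivation. HF admission dates are already needed for Secondary Endpoint #1. The documents describe medication review at clinic visits and recording of study-drug dose changes, but no dedicated field for the open-label start date, so its availability should be confirmed first. One small downside remains: a patient who was also becoming intolerant at the time of the switch keeps the last blinded dose. The change concerns analysis only and leaves patient care as it is.

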13.3 Tertiary Endpoints

1. Time to death
2. Time to first HF hospitalization
3. Time to death and first HF hospitalization
4. Total number of HF hospitalizations
5. Number of subjects on continuous inotropic therapy ≥ 7 days after discharge from the index hospitalization
6. Number of subjects, listed for transplant (status 1A, 1B or 1-4), transplanted or implanted with an LVAD
7. Change in eGFR and cystatin C levels compared to baseline. Renal function will be assessed at baseline, 4, 8, 12, and 24 weeks
8. Number of subjects with unanticipated use of IV diuretics (outpatient, ER or inpatient)
9. Change in AUC in the KCCQ at 4, 12 and 24 weeks compared to baseline
10. The change in the AUC for the ratio of NT-proBNP/BNP from baseline to 2, 4, 8, 12 and 24 weeks

13.4 Exploratory Endpoints

Modified Clinical Composite endpoint including Death, LVAD or Heart Transplant (including Listing status of 1A, 1B or 1-4), Multiple HF Hospital Admissions, Single HF admission

14 METHODS TO PROMOTE ADHERENCE

14.1 Protocol Training

Protocol training and adherence will be a major focus of the investigator training. Based on our experience in prior studies, identifying and correcting non-adherence is best accomplished in a stepped approach. The site will be responsible for managing subject compliance with study drug administration and visit compliance.

14.2 Data Quality Reports

Site personnel are responsible for ensuring that all procedures required by the protocol are performed as outlined and that the data is collected and reported accurately and per established guidelines. The CC will generate and review data quality reports and will follow-up with study site personnel as needed to ensure adherence. Routine data quality reports will also be provided to the sites. Significant non-adherence issues will be discussed with the Executive Committee.

15 SAFETY MONITORING AND REPORTING

15.1 Institutional Review Boards

All sites will submit the study protocol, consent form, and other study documents to their IRB for approval. The approval letter for each clinical center will be reviewed by the CC. Any amendments to the protocol, other than minor administrative changes, must be approved by each IRB before they are implemented.

15.2 Adverse Event Definition

An adverse event (AE) is any untoward medical occurrence associated with the use of a drug in a subject, whether or not considered drug or biologic related. An AE can therefore be any undesirable sign, symptom or medical condition occurring after starting study drug, even if the event is not considered to be related to the pharmaceutical product. Study drug includes the drug under evaluation, and any reference drug given during any phase of the trial.

15.3 Suspected Adverse Reaction Definition

A suspected adverse reaction (SAR) is any adverse event for which there is a reasonable possibility that the drug caused the event. "Reasonable possibility" suggests there is a causal

relationship between the drug and the adverse event. “Suspected adverse reaction” implies a lesser degree of certainty about causality than adverse reaction, which means any adverse event caused by a drug.

15.4 Serious Adverse Events (SAE)

An adverse event or suspected adverse reaction is considered serious if the investigator or sponsor believes any of the following outcomes occurred:

- Death
- Life-threatening AE: Places the subject at immediate risk of death at the time of the event as it occurred. It does not include an AE that, had it occurred in a more severe form, might have caused death.
- Persistent or significant incapacity or substantial disruption of the ability to conduct normal life functions.
- Inpatient hospitalization or prolongation of hospitalization.
- Congenital anomaly or birth defect.
- Important medical events that may not result in death, be life threatening, or require hospitalization may be considered a serious adverse event when, based upon appropriate medical judgment, they may jeopardize the subject and may require medical or surgical intervention to prevent one of the outcomes listed in this definition above.

This determination is based on the opinion of either the investigator or sponsor (e.g., if either believes it is serious, it must be considered serious).

15.5 Laboratory Test Abnormalities

For laboratory test abnormalities that meet the definition of an SAE, that required the subject to have the investigational product discontinued or interrupted or required the subject to receive specific corrective therapy, the clinical diagnosis rather than the laboratory term will be used by the reporting investigator (e.g., anemia versus low hemoglobin value).

15.6 Assessment of Causal Relationship

A medically-qualified investigator must assess the relationship of any AE to the use of study drug, based on available information, using the following guidelines:

- **Not related:** There is not a reasonable causal relationship to the investigational product and the adverse event.
- **Unlikely related:** No temporal association or the cause of the event has been identified, or the drug or biologic cannot be implicated.
- **Possibly related:** There is reasonable evidence to suggest a causal relationship between the drug and adverse event.
- **Related:** There is evidence to suggest a causal relationship, and the influence of other factors is unlikely.

15.7 Assessment of Adverse Event Severity

The determination of adverse event severity rests on medical judgment of a medically-qualified Investigator. The severity of AEs will be graded using the following definitions:

- **Mild:** Awareness of sign, symptom, or event, but easily tolerated;
- **Moderate:** Discomfort enough to cause interference with usual activity and may warrant intervention;
- **Severe:** Incapacitating with inability to do usual activities or significantly affects clinical status, and warrants intervention.

15.8 Expectedness

The expectedness of an AE or Suspected Adverse Reaction (SAR) shall be determined according to the most current patient package insert (PPI). Any AE that is not identified in nature, severity, or specificity in the current PPI is considered unexpected. Events that are mentioned in the PPI as occurring with a class of drugs or as anticipated from the pharmacological properties of the drug, but not specifically mentioned as occurring with the particular drug under investigation are considered unexpected.

15.9 Anticipated Disease Related Events and Events of Interest

The following are anticipated, disease-related events in patients with HF or anticipated events of interest in patients with heart failure taking valsartan or valsartan/sacubitril:

- **Arrhythmias:** This refers to both atrial and ventricular arrhythmias.
- **Sudden Cardiac Death:** This refers to witnessed cardiac arrests and sudden deaths without an otherwise apparent cause such as trauma or malignancy.
- **Acute coronary syndrome:** This refers to unstable angina, non ST segment elevation myocardial infarction (NSTEMI), and ST segment elevation myocardial (STEMI).
- **Unplanned hospitalization, ER visit or clinic visit for worsening HF:** This refers to treatment for acute heart failure such as receiving intravenous diuretics.
- **Cerebrovascular event:** This refers to cerebrovascular accidents (stroke) of any cause (hemorrhagic, ischemic, or embolic) and transient ischemic attack (TIA).
- **Venous thromboembolism:** This includes both deep venous thrombosis and pulmonary embolus.
- **Lightheadedness, Presyncope, or Syncope:** This includes dizziness, lightheadedness, or fainting from any cause.
- **Worsening renal function:** This refers to acute kidney injury, typically defined as a decrease in eGFR \geq 20% over 48 hours, or progressive loss of renal function over time.
- **LVAD implantation:** This refers to implantation of a temporary or durable LVAD.
- **Cardiac Transplantation**
- **Hyperkalemia \geq 5.5 mEq/L**
- **Acute renal failure with serum creatinine $>$ 2.5 mg/dL**
- **Angioedema**
- **Symptomatic hypotension**

Anticipated events will not be captured as AEs/SAEs during the study, but will be entered on the appropriate electronic case report form (eCRF) module (“Events of Interest” page).

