LCZ696 (sacubitril/valsartan): The use of LCZ696 compared to the guideline-indicated ACE inhibitor enalapril reduced mortality was shown in the PARADIGM trial to reduce the hazard ratio for cardiovascular death and mortality by 20%. The updated 2016 ACC/AHA/HFSA guidelines for the treatment of heart failure recommend the use of sacubitril/valsartan in patients with NYHA II-III heart failure (I, LOE B-R).⁵ Few enrollees in the PARADIGM trial had NYHA Class IV heart failure and enrollment required systolic blood pressure > 100 mmHg at the time of enrollment. The risks and benefits of LCZ696 among patients with advanced heart failure and lower enrollment blood pressure are not known, which is the rationale for this trial. The known risks of Entresto™ overlap with those of valsartan alone, with some initial considerations. In the PARADIGM trial, use of LCZ696 was associated with a greater incidence of angioedema than the comparator drug enalapril (0.5% vs. 0.2%). The risk of angioedema with LCZ696 compared to enalapril was relatively greater among Black patients (2.4% vs. 0.5%). Patients with a history of angioedema are contraindicated from taking this drug. Trial data indicate adverse reactions occurring ≥5% are hypotension, hyperkalemia, cough, dizziness, and renal failure. Symptomatic hypotension in PARAGON was more common among patients taking LCZ696 than enalapril (18% vs. 12%).

Use of drugs that act on the renin-angiotensin system during the second and third trimesters of pregnancy reduces fetal renal function and increases fetal and neonatal morbidity and death. Women of child-bearing potential must have a negative pregnancy test prior to initiating study drug. When pregnancy is detected, discontinue study drug as soon as possible. These adverse outcomes are usually associated with use of these drugs in the second and third trimesters of pregnancy. There is no information regarding the presence of sacubitril/valsartan in human milk, the effects on the breastfed infant, or the effects on milk production. Sexually active subjects must agree to use appropriate contraception as long as they are taking study drug. Medically acceptable contraceptives include:

- surgical sterilization (such as a tubal ligation or hysterectomy)
- approved hormonal contraceptives (such as birth control pills, patches, implants or injections)
- barrier methods (such as a condom or diaphragm) used with a spermicide, or
- Intrauterine device (IUD)

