15.10 Recording and Reporting of Adverse Events

The site Investigator is responsible for monitoring the safety of subjects enrolled into the study at the study sites. For this study, non-serious AEs will not be collected on the safety reporting page of the eCRF, but should be documented in the source documents and followed according to local standard of care. Events significant enough to necessitate modification of study drug dosing will be captured on the appropriate eCRF module (“Study Drug Dosing” page).

All SAEs, except for those anticipated events listed above, occurring from signed informed consent through study visit 11 will be captured on the SAE eCRF. Subjects that have screen failed will be followed for SAEs until two weeks post last study drug dose. Unless exempted as described above, all SAEs, whether or not deemed drug-related or expected, must be reported by the investigator or qualified designee within 24 hours of first becoming aware of the event. For this study, the cause of death will be reported on either the SAE or Events of interest (EVNINT) eCRF, as well as the Death eCRF page. The investigator or qualified designee will enter the required information regarding the SAE into the appropriate module of the eCRF, which will automatically result in distribution of the information to DCRI Safety Surveillance. DCRI Safety Surveillance will share all SAE reports with Novartis Pharmaceuticals. If the eCRF system is temporarily unavailable, the event, including the investigator-determined causality to study drug should be reported via the back-up paper SAE form to DCRI Safety Surveillance. Upon return of the availability of the electronic data capture (EDC) system, the SAE information must be entered into the eCRF.

Any misuse or abuse of the study drug, other medication errors and uses outside of what is foreseen in the protocol (irrespective of whether a clinical event has occurred) must also be reported to DCRI.

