15.12 Suspected Unexpected Serious Adverse Reaction

AEs that meet the criteria of serious, related to study drug, and unexpected per PPI, qualify for expedited reporting to the regulatory authorities. The site Investigator will assess all SAE's occurring at his/her site and evaluate for "unexpectedness" and relationship to study drug. The site Investigator is required to complete and submit a voluntary MedWatch Report for events confirmed by DCRI Safety Medical Monitor, as serious, study drug related and unexpected at: <https://www.accessdata.fda.gov/scripts/medwatch/>.

A copy of this report should be kept at the site and also forwarded to the DCRI Coordinating Center and to DCRI Safety Surveillance.

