16.3 Interim Analyses and Safety Reviews

Interim examinations of key safety and process data will be performed at regular intervals during the course of the trial. It is anticipated that the DSMB will review the accumulating data at predetermined intervals (approximately every 3 months). In addition, a summary of clinical events and adverse events will be sent to the Chair of the DSMB monthly for review. The DSMB will receive a full report 4 times each year and the Chair can call a meeting of the full DSMB at any time. The CC will create regular reports to track subject enrollment reports, rates of adherence with the assigned treatment strategy, and frequency of protocol violations. Prior to each meeting, the CC will conduct any requested statistical analyses and prepare a summary report along with the following information: subject enrollment reports, rates of adherence with the assigned treatment, and description of SAEs. The DSMB will review data masked by study group (such as X vs. Y). An interim review will be conducted using the first 200 patients randomized with analysis starting after the last of the 200 patients complete study follow-up.

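### Serious angioedema, which the protocol presents as a drug risk, is exempt from SAE capture and the 24-hour report, has no described route to central safety review, and has no named analysis

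*Protocol*

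**What the plan says.** Protocol 15.9 opens one list for two kinds of event: those expected from heart failure, and "anticipated events of interest in patients with heart failure taking valsartan or valsartan/sacubitril". Arrhythmia, worsening heart failure, LVAD implantation and transplantation stand beside angioedema, symptomatic hypotension, hyperkalemia and acute renal failure. The closing rule covers them all: "Anticipated events will not be captured as AEs/SAEs during the study, but will be entered on the appropriate electronic case report form (eCRF) module".

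Protocol 15.10 repeats the exemption for the SAE form, and again for the 24-hour clock: "Unless exempted as described above, all SAEs, whether or not deemed drug-related or expected, must be reported". It says that entering SAE information in the eCRF notifies the coordinating center's safety group automatically. That group shares SAE reports with the drug supplier. The paper back-up is also an SAE form.

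On expectedness, 15.8 says: "Any AE that is not identified in nature, severity, or specificity in the current PPI is considered unexpected". On expedited reporting, 15.12 says: "The site Investigator will assess all SAE's occurring at his/her site". A MedWatch report then needs confirmation by the safety medical monitor.

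The DSMB meeting report in 16.3 is listed as enrollment, "rates of adherence with the assigned treatment, and description of SAEs". SAP 13 compares SAEs only.

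**The concern.** Exempting events of the disease is sensible: in NYHA class IV patients, background illness would swamp SAE reporting. That reason does not extend to angioedema. Protocol 11.6 treats it as an effect of LCZ696, more frequent in Black patients, and says that risks and benefits in advanced heart failure with lower blood pressure are unknown.

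As written, a site that sees life-threatening angioedema completes the Events of Interest page. No 24-hour duty follows, and no described step alerts the safety group or the supplier. This matters more because SAP 14 sets no safety stopping guideline and leaves that decision to the DSMB's clinical opinion, which depends on what reaches the DSMB and how soon.

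**Working it through.** The plan states no figure for this point. The check is a side-by-side reading, followed by a calculation for scale only.

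**1. Can angioedema be serious under the protocol?** Yes. Section 15.4 counts death, immediate risk of death and hospitalization as serious, and excludes no listed event.

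**2. Does the exemption have a limit?** No. Neither 15.9 nor 15.10 makes an exception for seriousness, severity or causality.

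**3. Does an exempt event reach central safety review by another described step?** The only feed in 15.10 is SAE entry or its paper back-up. Section 15.6 asks for a causality judgment on any AE, but 15.9 says that listed events are not captured as AEs, and no step sends an Events of Interest entry to the medical monitor named in 15.12. Section 15.12 itself does not repeat the exemption. Sections 15.4, 15.9, 15.10 and 15.12 therefore do not fit together.

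**4. Does being anticipated settle expectedness?** No. Section 15.8 makes severity and specificity part of that test, so it has to be applied case by case.

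**5. Do planned analyses recover the listed drug effects?**

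| Listed event (15.9) | Named SAP analysis |
|---|---|
| Symptomatic hypotension | Secondary endpoint 3 (SBP ≤ 85 mmHg with symptoms) |
| Worsening renal function, acute renal failure | Secondary endpoint 4 (eGFR < 20, a related measure) |
| Hyperkalemia | Secondary endpoint 5 |
| Angioedema | None; SAP 13 covers SAEs only |

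**6. Run-in.** Every enrolled subject takes open-label LCZ696 for 3 to 7 days (7.1, 10.4). Angioedema at that stage falls under the same exemption. A subject who is not randomized is also outside the ITT population that 18.1 uses for safety analyses.

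**7. Scale.** Inputs:
- Rates p from 11.6, which come from another trial.
- n = 200 on LCZ696 (400 planned, 1:1), or about 183 (365 randomized per SAP 3, halved).

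Expected cases = n × p. Chance of at least one = 1 − (1 − p)^n.

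| n | p | Expected | At least one |
|---|---|---|---|
| 200 | 0.5% | 200 × 0.005 = 1.0 | 1 − 0.995^200 = 63% |
| 183 | 0.5% | 183 × 0.005 = 0.9 | 1 − 0.995^183 = 60% |
| 200 | 2.4% (if it applied to all) | 200 × 0.024 = 4.8 | 1 − 0.976^200 = 99% |

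The 4.8 is an expectation, not a maximum: with n = 200 and p = 2.4%, the binomial probability of 6 or more cases is 35%. Run-in and valsartan-arm cases are not counted. The documents do not say what fraction would be serious.

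**The case against.** The strongest reply is that the list is deliberate. Section 15.9 says openly that it covers events expected on either study drug, and the protocol describes the drug as already approved for NYHA class II to IV. That stands: this is a stated design choice, not a drafting slip. It does not explain why a life-threatening drug reaction needs no prompt central report.

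A reader might infer that such a case has no route at all to the unexpectedness assessment. The documents do not support that. Section 15.12 has the investigator assess SAEs without repeating the exemption, and 15.9 and 15.10 can be read as limiting only capture and the 24-hour report. What is missing is a described step. The package insert is not among the documents either, so whether a given severity goes beyond it cannot be judged here.

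A reader might also infer that the DSMB never sees these events, or that its opinion is the only protection. Neither follows. The Chair gets a monthly summary of clinical and adverse events and can convene the board at any time, and requested analyses are run before meetings (16.3). The DSMB reviews detailed safety data about every 3 months, and sites report AEs promptly to their IRB under local rules (15.11). Section 18.1 promises comparisons of AEs and laboratory values. Every death has its own eCRF page, and dose-changing events go on the dosing page (15.10). The medical monitor is contacted if unblinding is needed (10.9). These measures reduce the gap, but none is a 24-hour central report with causality.

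Nor is angioedema the only drug effect without prompt reporting: hypotension, hyperkalemia and renal failure are exempt too. The case for singling it out is that they, or related measures, are analyzed as endpoints and it is not.

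**Conclusion.** The point holds in this form. Angioedema shares an exemption whose rationale fits disease events. Serious cases are kept off the SAE form and outside the 24-hour rule, no described step takes them to the safety group or medical monitor, and no named analysis covers them. Events of Interest are also absent from the listed content of the DSMB meeting report, which is less than saying that the DSMB is unaware of them.

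The numbers are small and rest on an assumption. The 11.6 rates come from a different population and follow-up. This trial has an LCZ696 run-in before randomization, and it excludes hypersensitivity to the drugs and known contraindications such as hereditary angioedema. On that assumption, about one LCZ696 case is expected at 0.5%. A between-arm comparison would then say little, so timely review of individual cases is the useful safeguard. This is an inexpensive safety improvement that should be made. It casts no doubt on the efficacy analysis.

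**What to change.** - **Protocol 15.9 and 15.10:** exclude serious angioedema from the exemption, so that it goes on the SAE form with causality, expectedness and the 24-hour report, and is still recorded as an Event of Interest. Keep the exemption for events of the disease.
- **Protocol 15.4, 15.9, 15.10 and 15.12:** reconcile these so that it is clear which SAEs the investigator assesses for unexpectedness and how they reach the medical monitor.
- **Protocol 16.3 and SAP 13:** name Events of Interest, by masked arm in the DSMB meeting report and by arm in the safety section, with angioedema shown separately.
- **Subjects already followed:** the SAP gives 365 randomized and describes the interim analysis as done, so a new site instruction cannot work backwards. Review the Events of Interest entries centrally for serious angioedema, including the run-in.

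The cost is protocol and SAP wording, one central review, a handful of extra SAE reports and double entry for those cases. The form, the 24-hour route and the safety group already exist.
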